6.2.2 Eventual Appendectomy

Participants will be asked whether they have had an appendectomy at each contact through their four-week follow-up after the index diagnosis of appendicitis, and then surveyed at regular intervals to determine if they developed recurrent appendicitis and the resulting treatment (non-operative intervention, unplanned re-operative intervention, planned or elective appendectomy). With the participant's informed consent, the research coordinator will obtain all inpatient and outpatient medical records related to AEs or recurrent appendicitis and records will be abstracted to determine whether the AEs were associated with the incident appendicitis or whether recurrent appendicitis was confirmed. If recurrent appendicitis was confirmed, treatment and patient/clinician decision-making will be recorded on the EMR form.

Patients reporting eventual appendectomy will be surveyed to determine, from the patient perspective, the reason for eventual appendectomy.

7.0 Data Management and Information Security

7.1 Data Management

Data management will be the responsibility of the site investigators for data collected at their particular site, and the UW DCC for the combined data from all sites.

At sites, all study questionnaires completed in person or by phone (or by mail or email) will be reviewed by research coordinators for accuracy and completeness. Through the Week 2 follow-up and as needed subsequently through the 2-year follow-up, data collection is the responsibility of the study staff at the site under the supervision of the site investigator. During the study, the site investigator will maintain complete and accurate documentation for the study.

The UW DCC will provide support for data management, quality review, analysis, and reporting of the study data. The DCC will create the electronic study database using REDCap (Research Electronic Data Capture). REDCap is a secure web application for building and managing online surveys and databases.

Patient follow-up from 4-weeks on will be completed using customizable software from DatStat, Inc (Seattle, WA) to securely manage survey distribution methods, response data collection, and reporting. UW study staff will complete data audits to ensure data quality as well as accurate data-entry for surveys received by mail.

7.1.2 Data Quality Monitoring

The CCC and DCC will review participant enrollment, reasons for exclusion, participant demographics, and follow-up rates by site in order to assess proximity to enrollment targets, site performance, and protocol adherence.

In addition, the DCC will perform early quality assurance checks by running REDCap Data Quality reports. These reports include missing values for required fields, incorrect data

[name] Study Protocol Version 6.1 February 2019

type, range checks, outliers, hidden fields that contain values, and multiple choice fields with invalid values. Values that need to be corrected will be brought to the attention of the research staff at that site.

7.2 Information Security

Sites:

All participant data collected on paper at sites will be stored in locked file cabinets located in the site research offices.

All data entered onto laptop/desktop computers located at sites will be secured via each site's Information Security infrastructure. Information Security at all participating sites is multi-layered and includes physical security measures, network security measures, managed servers, and desktop/laptop computers with authentication and authorization controls. All systems are designed and implemented to properly secure restricted or confidential information, including PHI, from inadvertent or unauthorized disclosure. All policies and procedures adhere to federal, state, and health system requirements. Servers, desktops, and laptops are under active management by an Integrated Technology Services Group (ITSG) at each participating site. In addition to maintaining anti-virus and firewall installations, the ITSG audits patch status of systems connected to the network and installs any missing updates or patches found. Servers have defined change control periods for operating system maintenance but are patched or updated outside the schedule as necessary to address threats. Anti-virus software is configured to update daily. The host-based firewalls restrict inbound connections to only the subnets where department workforce resides or that are needed for firewall administration. The firewall rule set on the dedicated server is further restricted to the network subnets. A specific Windows domain account is required to access computers. Domain passwords must be at least 8 characters in length, conform to complexity rules, and be changed at least every 120 days. Database systems and security policies are established and overseen by administrative staff members who do not require research funding.

RedCAP:

All data, including PHI, names, and contact information will be entered onto a HIPAA and 21 CFR Part 11- compliant database. Participant PHI, including names, contact information, health information, will be entered onto this database. Only study staff will have access to the database and each study staff member will be given separate access only after completing study-required trainings.

DatStat:

Data Transmission and Storage

DatStat servers, databases, and web presences employ multiple forms of security features, while security protocols are designed to protect both the data itself, as well as the participants involved in data collection efforts.

DatStat secure servers are registered with site certificates provided by AddTrust that provide for advanced encryption over the wire. As each user moves through the survey form, his/her responses are encrypted while in-transit between the browser and DatStat's server using SSL (Secure Sockets Layer) and 40, 56, or 128-bit Public Key Encryption.

[name] Study Protocol Version 6.1 February 2019

All servers used for data collection are highly fault-tolerant and equipped with redundant, hot-pluggable power supplies, redundant network interfaces, and RAID 5 hot-swappable disk storage. All primary servers are plugged into a monitored, uninterruptible power supply (UPS).

Physical security

DatStat servers are stored in a locked server cabinet/rack, which are housed in a state-of-theart, well-ventilated data center. Physical access to servers and data backup is restricted to a minimal number of IT professionals. The facility is secured by guards who monitor all access to the building and will notify DatStat personnel of any building compromise or intrusion.

Logical security

In addition to the physical safeguards listed above, the data center is monitored 24/7 by Information Technology (IT) and security staff via equipment monitoring and Closed-Circuit Television. Servers are protected from remote attacks through use of dedicated hardware firewalls (Watchguard), with auditing enabled at the recommended settings. Watchguard LiveSecurity keeps IT staff advised of all known security alerts. Firewalls closely monitor traffic to block suspicious packets from access to all systems.

Security patches are applied to DatStat servers on a timely and ongoing basis. Logs are created by the web servers to increase accountability and are essential in investigating incidents after the fact. The following are logged: failed and successful logins, attempts to access files/ directories without authority, successful and failed attempts to access sensitive data.

8.0 Statistical Analysis Plan and Stopping Rules

8.1 Randomization Overview

This is a non-inferiority based, pragmatic, randomized controlled trial (RCT) of antibiotics versus appendictomy for the treatment of uncomplicated appendicitis with a concurrent observational cohort to characterize any selection bias associated with patients choosing to participate in the randomized trial, and to support the generalizability of study results. By necessity, this is an unblinded study (patients will know if they were randomized to appendectomy or antibiotics), and analysts will know the treatment allocation of study participants. The DCC will generate and maintain randomization lists for each practice site. We will use block randomization within practice sites, with random blocks of 4, 6, or 8 participants. Using block randomization ensures that equal numbers of participants are randomized to the intervention and control arm and that the two groups are balanced at periodic enrollment intervals. Crossover, in the conventional manner, is defined as a patient who is randomized to appendectomy who refuses to undergo surgery or someone who is randomized to antibiotics but chooses appendectomy before the antibiotics are started. For the sake of convenience in describing statistical analysis and data monitoring plans, we define the term early antibiotics failures (or treatment changed) as patients in the antibiotics treatment arm who were treated with appendectomy within four weeks after randomization.

8.2 Outcomes Measures

The primary analysis outcome is the EQ-5D at four weeks following randomization to treatment in the intention-to-treat (ITT) population. Important clinical endpoints include the following: complications or AEs associated with antibiotics or appendectomy; days until resolution of symptoms; rates of perforated appendicitis; rates of appendiceal cancer; hospital days; number of days using antibiotics beyond the initial treatment schedule; clinic visits; and caregiver/patient

"time in healthcare." Additional PRO measures include the 10 PROMIS Global Health Short Form, the Decision Regret Scale, and GIQLI.

8.3 General Analytic Strategy

The primary evaluation of EQ-5D at four-weeks will be conducted using an ITT analysis, where patients' data are analyzed according to the patients' randomized treatment assignment. Using this analytic approach in a non-inferiority study design comparing antibiotics treatment to appendectomy, we aim to test whether the global EQ-5D scores are not different by more than a margin of 5% (M = 5%). The margin (5%) was selected because it is within the meaningful clinical important difference (MCID) threshold of the EQ-5D, which is 5-10%.

1. Primary Analysis, Aim 1 - Patient-reported QoL, as measured by the EQ-5D at fourweeks, will be assessed using a linear regression model that adjusts for an indicator of randomized treatment group assignment and for all factors used to stratify randomization (e.g., practice site). As recommended by the United States Food and Drug Administration guidelines on clinical trial design. 26 the estimated treatment effect and 97.5% one-sided confidence interval (CI) will be compared to the non-inferiority margin (M = -5%). ²⁷⁻²⁹ We will conclude that antibiotics are non-inferior to appendectomy when the entire 97.5% one-sided confidence interval is greater than M (Figure 1, example trial conclusion A). This is equivalent to a one-sided (α=0.025) test of the null hypothesis H_0 : $\Delta < -5\%$, where Δ represents the difference in mean EQ-5D at four-weeks comparing the antibiotics treatment strategy to the appendectomy treatment strategy. If the null hypothesis of H_0 : $\Delta < -5\%$ is rejected at the final evaluation, we will conduct a test of superiority to determine the level of statistical evidence supporting an alternative hypothesis H_A : $\Delta > 0\%$ (Figure 1, example trial conclusion B). For Sub Aim 1, we will similarly evaluate non-inferiority on patient-reported QoL among the cohort without appendicolith.

[figure not shown]

Figure 1. Example Trial Conclusions in a Non-inferiority Trial.

2. Secondary Analysis, Aim 1 – Secondary analyses of the primary outcome measures will include examining the entire trajectory of EQ-5D QoL measurements for each patient using linear mixed effects models for longitudinal data.³⁰ While patient-elected changes in treatment and early antibiotics failures are anticipated, the ITT approach is an appropriate primary analysis. We will conduct a secondary as-treated analysis of the primary outcome measure that appropriately accounts for patient- or provider-level characteristics found to be differentially represented among patients in the antibiotics

[name] Study Protocol Version 6.1 February 2019

arm who are treated with appendectomy and those in the appendectomy arm who do not ultimately have surgery. Careful as-treated and secondary data analyses are of importance in understanding the effectiveness of the treatments and in assessing in which subgroups is the antibiotics treatment strategy most effective. A simple astreated analysis is problematic because randomization is broken when select patients in the antibiotics arm ultimately receive appendectomy or surgery-assigned participants who later choose to forego surgery. Thus, patients who are successfully treated with antibiotics and do not undergo appendectomy may differ demographically or clinically in ways that introduce bias in a naive as-treated analysis. Detry (JAMA 2014) recommends both an ITT and a careful as-treated analysis to address treatment changes in non-inferiority trials where non-adherence, crossover, or treatment changes are present. If we find a difference between the ITT and as-treated results, the ITT results will be considered the primary analysis. 32

We will consider a two-stage approach for this as-treated analysis to: 1) identify subgroups that are likely to require appendectomy, therefore, should not be considered as good candidates for treatment with antibiotics, and 2) estimate the complier average causal effect (CACE), which seeks to compare the outcomes of patients treated successfully in the antibiotics arm (i.e., did not ultimately have surgery) with patients randomized to the appendectomy arm who similarly would not have crossed over had they been randomized to the antibiotics arm. The CACE framework considers the ITT mean in each randomized arm as being comprised of two subgroup means: 1) patients who would be successfully treated with antibiotics without appendectomy and 2) patients who would eventually require appendectomy after being treated with antibiotics. We are able to directly observe which patients in the antibiotics arm ultimately cross over, but require the CACE framework to identify similar patients in the appendectomy arm. We will use a maximum likelihood mixture modeling approach to identify the optimal comparison group from the control arm for observed compliers in the intervention arm.³³ This application of mixture modeling permits an examination of two aspects of intervention process, the prediction of early antibiotics failures in the appendectomy group and the examination the treatment effect on QoL among patients who are suitable candidates for treatment with antibiotics.34,35

We will also compare secondary PROs (i.e., 10 PROMIS Global Health Short Form, GIQLI, and the Decision Regret Scale) using an ITT framework and linear regression models. Similar to the primary outcome measure, secondary PROs will be assessed using model-based point estimates and associated confidence intervals. The magnitude of effect will be judged a *posteriori* using margins that are of comparable magnitude as the EQ-5D in terms of the Cohen's d statistic. In an exploratory analysis, the complete longitudinal trajectory of all PRO metrics will be assessed with linear mixed effects models.

3. Exploratory Aim A – Using only data from patients enrolled in the antibiotics arm, we will also examine the association of these characteristics with eventual appendectomy. We will employ univariate logistic regression models to identify and characterize associations with unplanned appendectomy. If we find that a number of baseline characteristics are relevant and the rate of unplanned appendectomy is high enough (e.g., >10-15%), we will use multivariable analyses to compare these characteristics among those undergoing early appendectomy (defined within the first four weeks) and eventual appendectomy (after four weeks). Due to the potentially large number of input variables, interactions, and longitudinal assessments, we will also use modern model

development methods such as the least absolute shrinkage and selection operator (LASSO) with boosting. 36,37 Boosting provides a more sophisticated approach towards building multivariable predictive models and allows nonlinear relationships between the input variables and risk of requiring appendectomy after first being treated with antibiotics. Boosting is a multiple prediction and aggregation method for classification, where a "base learner" fitting method is fitted multiple times on reweighted data and a final estimator is constructed through a linear combination of the multiple estimates. Results of these analyses will be considered hypothesis generating and may support secondary studies aimed at predictive modeling.

- 4. Primary Analysis, Aim 2 Clinical endpoints (e.g., days until resolution of symptoms; rates of perforated appendicitis; extent of operation and surgical complications; complications associated with antibiotics; hospital days; number of days using antibiotics beyond the initial treatment; clinic visits; and caregiver/patient "time in healthcare") will also be compared between ITT groups using regression models appropriate to each endpoint (e.g., linear, logistic, Poisson, or Cox proportional hazards regression models), along with a similar non-inferiority framework with margins based on MCIDs. For Sub Aim 2 we will similarly compare clinical endpoints among the cohort without appendicolith.
- 5. Exploratory Aim B One assumption is that patients included in the RCT are sufficiently similar to those from the general population of patients with appendicitis. Using simple univariate descriptive and comparative statistics (e.g., t-tests, Chi-squared tests), we will compare randomized patients to those in the parallel observational cohort to identify selection bias. We will also compare the primary outcome measures between randomized and non-randomized patients by examining the entire trajectory of EQ-5D QoL measurements using linear mixed effects models for longitudinal data, providing an assessment of differences in the rate of change of QoL. We will adjust for patient- or provider-level characteristics found to be differentially represented in RCT. Using methods similar to those described in the plan for Aim 1 Secondary Analyses, we will adjust for treatment received to fully assess whether patients who participate in the RCT have a different outcome trajectory than patients in the observational cohort.

8.4 Missing Data

We will conduct a missing data analysis to describe and characterize enrolled participants who do not provide data due to attrition. As described by Molenberghs and Kenward (2007), we will use inverse probability weighting in secondary analysis within each longitudinal regression model to inflate the weights of cases that are under-represented in the analysis due to selective attrition and/or non-participation. We will also conduct sensitivity analyses using 10-fold multiple imputation to assess the robustness of the results when missing data are imputed. We will assess the sensitivity of inferences made from missing data first by using the two previously described methods for dealing with missing data and second, by imputing missing data under both pessimistic and optimistic scenarios to provide bounds on the statistical uncertainty. The characteristics of non-responders will be summarized in our final report and we will present the sensitivity of the estimated treatment effect due to alternative missing data methods.

8.5 Sample Size and Statistical Power

Prior studies suggest that non-clinical outcomes (e.g., loss of time from work and pain scores) were similar between groups, but did not evaluate a global QoL measure. The EQ-5D QoL

index ranges from 0 (worst QoL) to 1 (highest QoL), where anchor-based methods have shown that the MCID ranges 5%-10%. Based on data from a prior study of appendectomy with EQ-5D scores at 12 weeks, we estimate that the mean EQ-5D for appendectomy patients will be 0.90 with a standard deviation of 0.12. In order to assess QoL differences between interventions, we will recruit a total of 1552 patients assuming a 90% follow-up at four-weeks. This gives the study high power (>99%) to rule out EQ-5D differences between-groups as small as 5% (e.g., if we observe treatment differences of 0 to 2%) and 80% power if we observe a treatment difference of 3% (Table 5, below).

Previous Washington State evaluations of patients undergoing appendectomy (Table 1). identified that 2-3% of the population is African American, 10-12% Hispanic, 10-15% are Medicaid beneficiaries, and 10% will be above 64 years of age. Recruiting 1552 total patients will allow for a subgroup evaluation based on older age and Medicaid beneficiary status. Assuming 50% recruitment of these populations we anticipate including ~500 Medicaid beneficiaries and ~450 patients ≥65 years. As demonstrated in Table 5, this study also has adequate power (>80%) to rule out differences of 5% for observed treatment effect of Δ =0% within subgroups as small as n=250 patients, or treatment differences of Δ =-1% within subgroups of at least n=400. For this reason, we expect the study will be able to assess these two subgroups. All other subgroup evaluations will be post hoc and used for hypothesis development only.

Table 5. Statistical Power to Declare Non-inferiority on Patient-reported QoL, Overall and by

Subgroup (Non-inferiority Margin, M = -5%, one-sided α =0.025).

Treatment Difference A	Overall		Subgroups	
Treatment Difference, Δ	N=1552	N=250	N=400	N=500
-3%	82.6%	-	-	-
-2%	99.4%	-	57.1%	67.9%
-1%	100%	62.4%	83.8%	91.4%
0%	100%	83.0%	96.4%	98.8%

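### The ~450 older and ~500 Medicaid patients anticipated in section 8.5 do not follow from its own population shares; at those shares, power in the older subgroup is not secured

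*Protocol*

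**What the plan says.** Protocol section 8.5 sets the overall size: "we will recruit a total of 1552 patients assuming a 90% follow-up at four-weeks". It then describes the expected population, citing Table 1: "10-15% are Medicaid beneficiaries, and 10% will be above 64 years of age". From this it moves to subgroup counts: "Assuming 50% recruitment of these populations we anticipate including ~500 Medicaid beneficiaries and ~450 patients ≥65 years".

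The paragraph goes on to claim more than 80% power, against a difference of 5%, at Δ=0 "within subgroups as small as n=250 patients", and at Δ=-1% "within subgroups of at least n=400". It concludes: "For this reason, we expect the study will be able to assess these two subgroups". The next sentence sets these two subgroups apart from the rest: "All other subgroup evaluations will be post hoc and used for hypothesis development only".

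The All Sites row of Table 1 (section 3.2) shows 2200 cases a year, of whom 278 (12.6%) are over 65 and 558 (25.4%) are on Medicaid. Section 4.4.1 stratifies randomisation by site and appendicolith only. Neither document sets a quota or enrichment by age or insurance. The final SAP lists advanced age and insurance status under Additional Exploratory Subgroups, to be examined through treatment interactions.

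**The concern.** The counts are well above what the quoted shares would give in a trial of 1552. A 50% recruitment rate does not explain the gap by itself: applied to all patients alike, it leaves the shares unchanged. It raises the shares only if other patients enrol at a lower rate, and 8.5 does not say what that lower rate is.

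At stake is the standing of the only two subgroups that 8.5 expects to be able to assess. That expectation rests on counts of ~450 and ~500, both comfortably above the 250 and 400 thresholds. If enrolment follows the protocol's own shares, at least the older subgroup may be too small, and a reader would expect more precision there than the trial is likely to deliver.

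**Working it through.** **Inputs.** N=1552, 90% follow-up, SD 0.12 and control mean 0.90 (section 8.5); margin 5%, one-sided α=0.025 (Table 5 caption); 1:1 allocation (section 8.1); shares from 8.5 and from Table 1, All Sites row.

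**1. Shares implied by the stated counts.** 450/1552 = 29.0%; 500/1552 = 32.2%.

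**2. Counts under proportional enrolment (1552 × share).**
- Older: 0.10 × 1552 = 155; (278/2200) × 1552 = 196.
- Medicaid: 0.10 × 1552 = 155; 0.15 × 1552 = 233; (558/2200) × 1552 = 394.

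**3. Reproducing ~450 and ~500.** At the text's shares they can be reached. With a 10% older share, 450/(0.5 × 0.10) = 9000 patients in the pool. Then 500/(0.5 × 9000) = 11.1% Medicaid, which lies within 10-15%. But 1552/9000 = 17.2% overall, so older patients would enrol at 50% against (1552-450)/(9000-900) = 13.6% for everyone else. The pool of 9000 is a back-calculation and does not appear in the protocol.

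At Table 1's volumes no single period gives both counts. Half of 278 is 139 a year, so 450 older patients take 450/139 = 3.24 years, by which time Medicaid would be 279 × 3.24 = 904. Reaching 500 Medicaid takes 500/279 = 1.79 years, when older patients would number 139 × 1.79 = 249.

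**4. Size of the differential needed.** The enrolment-rate ratio, group against everyone else, is the odds of the needed share divided by the odds of the population share.
- Older: 3.7 at 10%, 2.8 at 12.6%.
- Medicaid: 4.3 at 10%, 2.7 at 15%, 1.4 at 25.4%.

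**5. Power.** With n = 0.9N/2 per arm, the noncentrality is (margin - |Δ|)/(0.12 × √(2/n)), referred to a noncentral t with 2n-2 degrees of freedom. The protocol does not say whether 5% is absolute (0.05) or relative to the mean of 0.90 (0.045), so both are run, with Δ on the matching scale.

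Check against the plan. The relative scale reproduces the total: margin 0.045 with Δ=-0.027 gives 698 per arm for 80% power, and 1396/0.9 = 1551.1, hence 1552. Neither scale reproduces Table 5 exactly, but the two bracket it: N=250, Δ=0 gives 80.0% (relative) and 87.5% (absolute) against the printed 83.0%; N=400, Δ=-1% gives 81.0% and 88.4% against 83.8%.

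Example, N=196, Δ=0: n = 88.2 per arm, standard error 0.12 × √(2/88.2) = 0.0181, noncentrality 2.49 (relative) or 2.77 (absolute), power 69.7% or 78.6%.

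| Subgroup count (source of share) | Power at Δ=0, relative to absolute margin | Power at Δ=-1%, relative to absolute margin |
|---|---|---|
| Older 155 (8.5, 10%) | 59-69% | 42-50% |
| Older 196 (Table 1, 12.6%) | 70-79% | 51-60% |
| Medicaid 155 (8.5, 10%) | 59-69% | 42-50% |
| Medicaid 233 (8.5, 15%) | 77-85% | 58-67% |
| Medicaid 394 (Table 1, 25.4%) | 94-98% | 80-88% |

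**6. Check that needs no choice of margin scale.** Take Table 5's own N=250 cells (83.0% and 62.4%) and scale the noncentrality by √(196/250). At Δ=0: (0.954 + 1.960) × 0.885 - 1.960 = 0.62, or 73%. At Δ=-1% the same step gives 52%. Both fall inside the ranges above.

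**The case against.** **The 50% rate is stated, and it is specific to these groups.** This is true, and step 3 shows that the counts can be produced from it. A reader might infer a plain arithmetic slip or an impossible figure; the documents do not support that. What they lack is the pool or overall rate that turns 50% into a severalfold differential, and any reason to expect one.

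**The power loss depends on the basis.** This stands in part. With an absolute margin and no allowance for loss, 196 older patients give about 83% at Δ=0. But the protocol itself assumes 90% follow-up, and with that the figure is below 80% on both margin scales and when scaled from Table 5.

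**Medicaid is not clearly short.** This stands. A reader might infer that both subgroups are underpowered. At Table 1's share (394) Medicaid reaches at least 80% at both Δ values; at 15% the answer at Δ=0 depends on the margin scale; only near 10% is the shortfall firm.

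**Age definition and site mix.** These also stand as limits. Table 1 counts >65 while 8.5 uses ≥65 and above 64, so 196 is slightly low. Reaching 250 would need 250/1552 = 16.1%, against 12.6%. Table 1 lists 12 potential sites, and up to 20 will be considered. Some site profiles would give 250 of each: the Skagit Valley row has 22.6% and 18.3%, or 351 and 284 of 1552. A reader might also split Table 1 by state to test the text's shares, but the table does not label sites by state, so no such figure is used here.

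**Little depends on it.** This is correct for the primary analysis, and the final SAP already classes both factors as exploratory.

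**Conclusion.** The concern holds as a minor one. The counts of ~450 and ~500 do not follow from the shares in 8.5 or Table 1 unless these patients enrol at about 2.8-3.7 times (older) and 1.4-4.3 times (Medicaid) the rate of everyone else, and that differential is neither stated nor justified. Proportional enrolment gives about 155-196 older and 155-394 Medicaid patients.

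The firm consequence is for older patients, whose expected number is below the protocol's threshold of 250 at either share. For Medicaid the conclusion turns on which share is right. These results assume SD 0.12, 90% follow-up, one-sided α=0.025 and enrolment proportional to the quoted shares. Because the site mix is not fixed, subgroup power is not secured, which is different from unattainable. Nothing here bears on N=1552, the margin or the primary conclusion.

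**What to change.** In section 8.5:

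1. Reconcile the text's shares with the All Sites row of Table 1, and use one age definition throughout.
2. Replace ~450 and ~500 with counts derived from the reconciled shares and 1552 (about 196 and 394 at Table 1's mix), or state and justify the pool and the differential uptake assumed.
3. Restate subgroup power at those counts, naming the margin scale and the follow-up rate used.
4. Keep the claim of more than 80% power only for a subgroup and Δ where the restated power supports it. Describe any other as exploratory, as the final SAP already does for age and insurance status.

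This changes wording only. Sample size, margin, α and the primary analysis stay as they are. The cost is a less favourable statement of subgroup power.
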